### 6.3 OUTCOME MEASURES

1. Hidradenitis suppurativa clinical response score (HiSCR)
2. Hidradenitis suppurativa – Physician’s global assessment (HS-PGA)
3. International Hidradenitis Suppurativa Severity Score System (IHS4)
4. Pain score (NRS30)
5. Number of abscesses and nodule counts at each visit
6. Number of flare ups as well as location of flare ups

### 6.4 STUDY TYPE & DESIGN & SCHEDULE

#### 6.4.1 STUDY ASSESSMENTS

##### 6.4.1.1 SUBJECT DEMOGRAPHICS

Demographic and baseline characteristics to be collected on participants include: Date of birth, gender, ethnicity and child-bearing potential (for females only).

20 participants will be recruited and divided into intervention and controlled group in a 1:1 ratio.

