## 2. STUDY SYNOPSIS

Provide brief information

Title:	Hidradenitis suppurativa treated with follicular unit excision: A prospective controlled pilot study
Short Title:	Hidradenitis suppurativa treated with follicular unit excision: A prospective controlled study
Design:	Open-label, interventional
Study Centres:	Sinclair Dermatology, Melbourne Australia
Hospital:	
Study Question:	How effective is follicular unit excision for the treatment of mild-moderate hidradenitis suppurativa?
Study Objectives:	
Primary Objectives:	The study's primary objective is to determine change in several hidradenitis suppurativa assessment scores score throughout follow-up visits in the first 24 weeks after follicular unit excision
Secondary Objectives	
 
i) To compare the changes in Hidradenitis Suppurativa assessment scores between intervention and control groups up to 24 weeks and on the treated sites before and after follicular unit extraction
 
ii) To compare the number of disease flares between the treated and control groups for 24 weeks after treatment
 
iii) To determine if specimens contain hair follicles, sebaceous glands, apocrine glands and eccrine glands on histopathology
 

Key Inclusion Criteria:	
 
i) Patients aged <math>\geq 18</math> years with hidradenitis suppurativa
 
ii) Mild-moderate hidradenitis suppurativa defined by Hurley stage 1 up to 2A
 
iii) Minimum diagnosis of 3 months prior to baseline
 
iv) Active hidradenitis suppurativa present for <math>\geq 3</math> months from initial diagnosis
 

Key Exclusion Criteria:	
 
i) Current treatment with systemic antibiotics, retinoids, immunosuppressants or biologic agents at discretion of the investigator
 
ii) Extensive scarring
 
iii) Absence of terminal hairs in target areas
 
iv) Previous laser hair removal in target areas
 
v) Pregnant or lactating women
 

Number of Planned Participants :	24
Investigational procedure:	Follicular unit excision using 0.8 mm Ertip® punch
Data analysis	The primary objective is to evaluate the efficacy of follicular unit excision in the treatment of adults with mild to moderate hidradenitis suppurativa. The primary analysis will be conducted to assess the primary and secondary endpoints once all participants have completed the Week 24 visit.
Safety considerations:	

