#### 6.4.1.6 MANAGEMENT OF FLAREUPS

Participants may be given medications to prevent flares to stabilize the condition prior to follicular unit extraction. This may be resorcinol 15% cream and/or oral antibiotics such as doxycycline 100mg. Often, flareups may need surgical management or intralesional corticosteroids. These are given as part of standard routine care to minimize flare-ups for the hidradenitis suppurativa and alleviate symptoms for patients and is part of management guidelines.

Participants may be given a sheet to document their flareups (Appendix 3). Participants may take photos of the flareups on their phone to show to the investigator but this is optional only. Investigators will not be collecting photos taken by participants.

Participants are divided into the intervention group and control group. The control group will be managed with topical clindamycin. A staff member of Sinclair Dermatology not involved in this study will randomise participants into the intervention and controlled group using the program from [www.randomizer.org](http://www.randomizer.org) in a 1:1 stratification ratio. The treatment group will be treated with follicular unit extraction. Due to the study design (the intervention being surgical and the controlled group being a topical application), investigators and participants are unable to be blinded as to which participants will be in the treatment or control group. As there will be 24 participants in this study, numbers 1-24 will be randomly allocated to either control or treatment group using [randomizer.org](http://randomizer.org) prior to recruitment of the study. Participants will then be allocated a number in the order in which they are recruited in the study and subsequently will be placed in the group that the number has been randomised into.

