## 7. STUDY POPULATION

This study will enroll male and female patients aged ≥18 years who are diagnosed with mild to moderate HS.

The study will consist of 24 recruited participants.

**Study Name:** Hidradenitis suppurativa treated with follicular unit excision: A 24-week prospective study

**Protocol Number:** FUEHS001

**Version & date:** version 1.3, dated 3rd February 2024

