## 8.4 REPLACEMENTS

There will be no replacements if participants withdraw.

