# 9. STATISTICAL METHODS

## 9.1 SAMPLE SIZE ESTIMATION & JUSTIFICATION

Given that this is a pilot study assessing the effectiveness of FUE for HS management, we have decided 24 participants is required as a pilot. The result of this study will be used to inform sample size calculations for future studies as well as account for 20% rate of lost to follow-up.

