## 9.2 POWER CALCULATIONS

This pilot study uses 12 participants in each group (intervention vs controlled) and results from this will allow us to calculate the sample size required for statistical power in future clinical studies.

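### Section 6.4.1.1 recruits 20 participants, while the synopsis, the randomisation text and the sample size section all plan 24

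*Protocol*

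**What the plan says.** Section 6.4.1.1 of the protocol (Subject demographics) states: "20 participants will be recruited and divided into intervention and controlled group in a 1:1 ratio". That is 10 per group.

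Every other statement of the size gives a different number:

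- Section 2 (Synopsis): "Number of Planned Participants : 24".
- Section 6.4.1.6: "As there will be 24 participants in this study, numbers 1-24 will be randomly allocated to either control or treatment group". Section 6.6 (Randomisation) repeats this sentence. Both sections say the list is made before recruitment and that participants take numbers in the order in which they are recruited.
- Section 7 (Study population): "The study will consist of 24 recruited participants".
- Section 9.1: "we have decided 24 participants is required as a pilot".
- Section 9.2: 12 participants in each of the two groups.

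Two further statements bear on how many participants reach Week 24. Section 9.1 says that the results will inform sample sizes for future studies, "as well as account for 20% rate of lost to follow-up". Section 8.4 says: "There will be no replacements if participants withdraw".

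**The concern.** The recruitment number is a basic design parameter, and this protocol fixes it twice with different values. Sections 6.4.1.1 and 7 both speak of participants recruited. The lower figure therefore cannot be read as the number expected to complete, with the higher one as the number enrolled, unless the text is changed.

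A site that followed 6.4.1.1 would stop four participants short of the randomisation list prepared under 6.4.1.6 and 6.6. The unused numbers would be the last four, whatever groups they belonged to. No blocking within the list is described, so the 1:1 split that 6.4.1.1 asks for would then depend on chance.

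Sections 9.1 and 9.2 give the purpose of the pilot as informing the sample size of later studies, so the number of participants contributing data matters even without a power claim. Section 9.1 is also unclear on this, because one sentence runs future planning and the 20% loss together.

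**Working it through.** **The plan's own arithmetic.** Section 9.2 gives 12 per group, and 12 + 12 = 24. This reproduces the total in 9.1 and agrees with the synopsis and sections 6.4.1.6, 6.6 and 7. The protocol gives no significance level, power, effect size or SD, so 24 cannot be checked against a power formula.

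**The conflict.** 24 − 20 = 4 participants, and 4/24 = 16.7% of the planned sample.

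**Effect on precision.** For a two-sample comparison with common SD, the 95% half-width in SD units is t(0.975, n1+n2−2) × √(1/n1 + 1/n2). The protocol does not state a precision; this only puts the four participants on a scale.

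| Scenario | n per arm | Half-width (SD) |
|---|---|---|
| 24 recruited, no loss | 12/12 | 2.074 × √(2/12) = 0.85 |
| 20 recruited, no loss | 10/10 | 2.101 × √(2/10) = 0.94 |
| 24 recruited, 20% loss | 10/9 | 2.110 × √(1/10 + 1/9) = 0.97 |
| 20 recruited, 20% loss | 8/8 | 2.145 × √(2/8) = 1.07 |

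The fair comparisons are 0.85 against 0.94 (no loss) and 0.97 against 1.07 (20% loss). Each is a widening of about 10%. Comparing 0.85 with 1.07 would mix the effect of recruiting fewer with the effect of loss.

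**Effect on balance.** Assume the list holds 12 numbers per group in unrestricted random order. The first 20 numbers then split as follows, out of C(24,20) = 10,626 equally likely sets:

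- 10:10: C(12,10)² = 66² = 4,356, probability 0.410; half-width 0.940 SD.
- 11:9 either way: 2 × C(12,11) × C(12,9) = 2 × 12 × 220 = 5,280, probability 0.497; half-width 0.944 SD.
- 12:8 either way: 2 × C(12,12) × C(12,8) = 2 × 1 × 495 = 990, probability 0.093; half-width 0.959 SD.

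The three counts sum to 10,626. Exact 1:1 is therefore less likely than not, but 10:10 or 11:9 together have probability 0.907, and the worst case costs only 0.02 SD in half-width.

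**Expected completers, if the 20% refers to this study.** 24 × 0.8 = 19.2, about 19, or 9.6 per group. Had only 20 been recruited, 20 × 0.8 = 16.

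**The case against.** The strongest reply is that 24 is plainly the intended number. It appears in five places besides 9.2, and the randomisation text, which governs what the site does, fixes numbers 1 to 24. The 20 in 6.4.1.1 is probably a leftover, the practical risk is low, and even if recruitment stopped at 20 the cost in precision and balance would be modest. This stands as a comment on size. It does not remove the contradiction, since the sentence in 6.4.1.1 is current text and taken alone would end recruitment four participants early.

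A reader might go further and infer a faulty dropout adjustment: that 20 was the evaluable target, that 24 came from 20 × 1.2 = 24 when 20/0.8 = 25 was needed, and that 24 × 0.8 = 19.2 therefore falls short. The documents do not support this. No evaluable or completer target is stated, and 6.4.1.1 calls the 20 recruited. The origin of 24 is not explained. Even on that conjecture the gap would be one participant (24 against 25, or 19 against 20). The 20% in 9.1 follows a reference to future studies and may belong to them. Without a stated target, the ban on replacements in 8.4 leaves no declared number unmet.

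A reader might also infer that the plan claims more precision or power than it can deliver. Section 9.2 claims neither, despite its heading.

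**Conclusion.** The point holds as a contradiction in the number to be recruited: 20 in section 6.4.1.1 against 24 everywhere else. Following the lower figure would lose 4 of 24 participants (17%) and widen a between-arm 95% interval by about a tenth (0.85 to 0.94 SD before loss). The stated 1:1 split would also be left to chance, with 10:10 at about 41% but serious imbalance unlikely. The precision figures assume a two-sample comparison with common SD; the balance figures assume a 12:12 list without blocking.

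That 24 is the intended number is an inference from its predominance and from the randomisation list, but a strong one.

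The 20% loss is a secondary matter of unclear wording, not a second inconsistency.

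**What to change.** In section 6.4.1.1, change 20 to 24 and state 12 per group, so that it matches the synopsis, sections 6.4.1.6, 6.6 and 7, and sections 9.1 and 9.2.

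In section 9.1, split the last sentence so that it says whether the 20% loss to follow-up is expected in this study or is to be allowed for in later ones. If it applies here, add that with no replacements (section 8.4) about 19 of the 24 are expected at Week 24. The sponsor must confirm which meaning was intended. A stated interval width is optional and not needed to repair the text.

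Both changes are wording only. They add no participants to the 24 already planned and do not alter the randomisation list, although they need the usual ethics committee approval of an amendment (section 14.4).

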##### 6.4.1.2 MEDICAL HISTORY

Medical history and current medical conditions will be collected. Only data up to 6 months prior to signing of the informed consent and until the start of study treatment is required. Whenever possible, diagnoses and not symptoms will be recorded.

##### 6.4.1.3 CONCOMITANT TREATMENT

All treatments administered during the 6 months prior to start of study treatment (including any treatment started during the screening period) will be collected.

##### 6.4.1.4 PHYSICAL EXAMINATION

A physical examination, including general appearance, will be performed. If indicated, based on medical history and/or symptoms, additional exams will be performed at the discretion of the investigator.

Information for all physical examinations must be included in the source documentation at the study site. Significant findings that are present prior to the informed consent by the subject must be included in the Medical History. Significant findings made after the signing of the informed consent that meet the definition of an adverse event will be recorded.

#### 6.4.1.5 PHENOTYPE BASELINE

The HS of the participants will be documented in the screening visit to identify its phenotype as follicular vs inflammatory (See Appendix 1).

#### 6.4.1.6 MANAGEMENT OF FLAREUPS

Participants may be given medications to prevent flares to stabilize the condition prior to follicular unit extraction. This may be resorcinol 15% cream and/or oral antibiotics such as doxycycline 100mg. Often, flareups may need surgical management or intralesional corticosteroids. These are given as part of standard routine care to minimize flare-ups for the hidradenitis suppurativa and alleviate symptoms for patients and is part of management guidelines.

Participants may be given a sheet to document their flareups (Appendix 3). Participants may take photos of the flareups on their phone to show to the investigator but this is optional only. Investigators will not be collecting photos taken by participants.

Participants are divided into the intervention group and control group. The control group will be managed with topical clindamycin. A staff member of Sinclair Dermatology not involved in this study will randomise participants into the intervention and controlled group using the program from [www.randomizer.org](http://www.randomizer.org) in a 1:1 stratification ratio. The treatment group will be treated with follicular unit extraction. Due to the study design (the intervention being surgical and the controlled group being a topical application), investigators and participants are unable to be blinded as to which participants will be in the treatment or control group. As there will be 24 participants in this study, numbers 1-24 will be randomly allocated to either control or treatment group using [randomizer.org](http://randomizer.org) prior to recruitment of the study. Participants will then be allocated a number in the order in which they are recruited in the study and subsequently will be placed in the group that the number has been randomised into.

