#### 6.4.1.8 HIDRADENITIS SUPPURATIVA SEVERITY ASSESSMENT

As part of standard routine care, participants will have the Hurley Stage of their HS, nodule count and abscess count documented at baseline. This is part of standard routine care to assess whether treatment is effective, and it will also allow us to calculate the hidradenitis suppurativa clinical response (HiSCR). HiSCR is defined as a  $\geq 50\%$  reduction in inflammatory lesion count (abscesses and inflammatory nodules), and no increase in abscesses or draining fistulas when compared with baseline. Participants will also have their hidradenitis suppurativa-physician's global

assessment (HS-PGA) and International Hidradenitis Suppurative Severity Score System (IHS4) score documented in follow-up visits. Pain will be assessed using the numerical scale 30 (NRS30) pain score (See Appendix 1).

These assessments will be done at week 0, week 6, week 12 and week 24.

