##### 6.4.2.1 SCREENING

All participants will be screened prior to enrolment in the study. The following procedures must be conducted at the screening visit.

- Written informed consent
- Review of eligibility (diagnosis, inclusion and exclusion criteria)
- Medical history (including previous psoriasis treatments)
- Physical Examination
- Vital Signs (Respiratory rate, heart rate, tympanic temperature, blood pressure)
- Weight
- Height
- HS severity score baseline measurements

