##### 6.4.2.2 VISIT 1 (WEEK 0)

This visit occurs no later than 28 days from Screening visit. The visit may occur on the same day as the screening visit provided i) the participant was given sufficient time to read through the patient information and consent form and ii) seek advice from their primary physician, family and/or friend and iii) have had their questions answered by the investigator adequately.

- Review of inclusion and exclusion criteria

- Review of medical history
- Review of adverse events (if any)
- Concomitant medication collection
- Vital Signs (Respiratory rate, heart rate, tympanic temperature, blood pressure)
- Physical Examination
- Weight
- Review of HS progress
- Follicular unit extraction and sample analysis (if intervention group)
- HS severity score assessments

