### 6.5 STANDARD CARE AND ADDITIONAL TO STANDARD CARE PROCEDURES

Standard Care Procedures		
Procedure	Time/Visit	Dosage/Volume
Resorcinol 15%/topical clindamycin	Week 0	Applied to affected area as needed when there is flare.

Additional To Standard Care		
Procedure	Time/Visit	Dosage/Volume
FUE	Visit 1	NA

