## 7.3 EXCLUSION CRITERIA

Participants fulfilling any of these criteria are not eligible for inclusion in this study:

1. Current treatment with antibiotics, retinoids, immunosuppressants or biologic agents at the discretion of the investigator/research team.
2. Extensive scarring.
3. Absence of terminal hairs in target areas.
4. Previous laser hair removal in target areas.
5. Pregnant or lactating women.

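### Baseline is not tied to one visit, so improvement from treatment given before follicular unit excision can be counted as response to the procedure

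*Protocol*

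**What the plan says.** **Baseline.** Section 6.4.2.1 lists "HS severity score baseline measurements" among the screening procedures. Section 6.4.1.8, which governs the severity scores, leaves screening out of its schedule: "These assessments will be done at week 0, week 6, week 12 and week 24". That section defines HiSCR relative to baseline but does not say which visit this is. Under 6.4.2.2, Visit 1 (Week 0) comes at most 28 days after screening and may be on the same day. Appendix 2 schedules the scores at both visits.

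**Treatment before the procedure.** Section 6.4.1.6 states: "Participants may be given medications to prevent flares to stabilize the condition prior to follicular unit extraction". It continues: "This may be resorcinol 15% cream and/or oral antibiotics such as doxycycline 100mg". No start, duration or end is given. Section 6.4.1.3 foresees that treatment may begin during screening. FUE takes place at Visit 1 and only in the intervention group (6.4.2.2, Appendix 2).

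**Allocation.** The numbered list is drawn up before recruitment, and participants take numbers in order of entry (6.4.1.6, 6.6). The number is assigned after consent (6.4.2). Investigators and participants are not blinded.

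**Medication and comparator.** Section 7.3 excludes "Current treatment with antibiotics, retinoids, immunosuppressants or biologic agents", qualified by investigator discretion; the synopsis restricts the antibiotics to systemic ones. Section 8.2.1 allows withdrawal for medication that may interfere with the measurements. On the comparator, 6.4.1.6 says "The control group will be managed with topical clindamycin", and 7.4 and 8.3.5 also name clindamycin alone, while the hypothesis in 6.1 names resorcinol/clindamycin.

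**The concern.** Change scores and HiSCR depend on the reference visit. The protocol offers two candidates and permits active treatment that could fall between them. An analyst who follows the label in 6.4.2.1 would measure change from before that treatment. One who follows the schedule in 6.4.1.8 would measure it from after.

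The stabilising treatment is described as preparation for a procedure that controls never have, and the arm can be known when the decision to stabilise is made. Under a screening baseline, improvement due to resorcinol or an antibiotic could therefore enter the FUE result and be read as an effect of the procedure. At stake are the before-and-after estimate on treated sites, the comparison with control, and the planning figures that 9.1 and 9.2 intend to take from this pilot.

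**Working it through.** The protocol gives no figure for this point, so there is none to reproduce. The check is how far a fall in lesions before FUE moves the response threshold under each baseline.

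**Inputs**
- HiSCR count component: a fall of at least 50% in abscesses plus inflammatory nodules from baseline (6.4.1.8).
- Interval from screening to Week 0: 0 to 28 days (6.4.2.2).
- Group size: 12 (9.2).
- s, the fractional fall in lesion count between screening and Week 0: not given in the protocol, so assumed over 0 to 50%.

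**Screening as baseline.** With screening count N, the Week 0 count is N(1 − s). Response requires a count of 0.5N or less. The further fall needed after FUE, relative to Week 0, is 1 − 0.5/(1 − s).

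**Week 0 as baseline.** The further fall needed is 50% whatever s is. Relative to screening, the total fall is then 1 − 0.5(1 − s).

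| Assumed fall before FUE, s | Further fall needed, screening baseline | Further fall needed, Week 0 baseline | Total fall from screening, Week 0 baseline |
|---|---|---|---|
| 0% | 50% | 50% | 50% |
| 10% | 44.4% | 50% | 55% |
| 20% | 37.5% | 50% | 60% |
| 30% | 28.6% | 50% | 65% |
| 40% | 16.7% | 50% | 70% |
| 50% | 0% | 50% | 75% |

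For s = 30%: 1 − 0.5/0.7 = 0.286.

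**One participant, for illustration.** Take 6 inflammatory nodules at screening and 3 at Week 0, with no abscesses or tunnels. The fall is (6 − 3)/6 = 50%, so the count component is already met. On the Appendix 1 scales, IHS4 goes from 6 (moderate) to 3 (mild) and HS-PGA from 3 to 2, all before FUE. If the count stays there to a follow-up visit, the participant is a responder against screening and shows no change against Week 0. Each such participant moves the response rate of a 12-person group by 1/12 = 8.3 percentage points. The protocol gives no basis for saying how many there would be.

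**Medication passages side by side.** Section 6.4.1.6 permits oral antibiotics before FUE. Section 7.3 makes current antibiotics an exclusion at the investigator's discretion, and 6.4.2.2 has eligibility reviewed again at Visit 1, the day of FUE. A participant stabilised on an oral antibiotic could therefore meet an exclusion criterion that day. Under 8.2.1 the same drug could later be a reason for withdrawal.

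**The case against.** Several points on the other side are fair.

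- **Timing.** Section 6.4.1.6 says only that treatment may precede FUE. It could precede screening as well, and if both visits are on one day there is no gap. This stands: treatment between the visits is permitted, not prescribed.
- **One arm only.** A reader might infer that only FUE participants are stabilised, so that the arms differ by more than FUE. The text does not say so. It speaks of participants in general and calls such treatment routine care; 6.5 and 8.1 do not limit standard care or anti-inflammatory medication to an arm. Asymmetry is possible, because the treatment is tied to FUE and allocation can be known, but it is not established. Any false-positive rate computed for a shift in the FUE arm alone would assume it.
- **Week 0 may be intended.** The section on severity scoring starts there. If Week 0 is the baseline, pre-FUE treatment earns no credit and instead lowers the starting score. This also stands, but 6.4.2.1 still attaches the baseline label to screening.
- **Medication conflict.** A reader might see a flat contradiction. The exclusion is discretionary, the withdrawal rule is permissive, and resorcinol is not on the exclusion list. The passages need reconciling, but do not exclude each other outright.
- **Visit 1 order.** FUE is listed before scoring, but the list states no sequence and scoring comes last at every visit. It does not show that scores are taken after the procedure; equally, nothing requires them before it.
- **Comparator.** Section 6.5 lists "Resorcinol 15%/topical clindamycin" as standard care for flares and does not define the comparator. The direct discrepancy is between 6.1 and 6.4.1.6, 7.4 and 8.3.5.
- **Size.** The lesion fall is assumed, would have to last to a follow-up visit, and HiSCR also requires no increase in abscesses or draining fistulas.

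**Conclusion.** The concern holds in conditional form. Baseline is fixed inconsistently, and the protocol permits treatment before FUE that is not bounded in time. Two conditions must both be met for bias: treatment falls between screening and Week 0, and screening is used as the baseline. Its effect can then be counted as FUE response, with the HiSCR count threshold dropping from a 50% further fall to 28.6% at an assumed 30% fall before FUE, and to zero at 50%. The documents do not support the stronger conclusion that change from baseline will credit other treatment to FUE.

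This should be corrected before scores are analysed: the choice of visit can change a participant's response status, and each changed status is worth 8.3 points in a group of 12.

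**What to change.** 1. Define baseline, for every score and in both arms, as the Week 0 assessment recorded before local anaesthetic, FUE or the first study topical. Use this definition in 6.4.1.8, including the HiSCR definition.
2. In 6.4.2.1, relabel the screening scores as screening scores.
3. State in the Visit 1 list (6.4.2.2) that scoring precedes the procedure.
4. Reconcile 6.4.1.6, 7.3, the synopsis exclusion wording and 8.2.1 on medication before FUE and during the study.
5. Reconcile 6.1 with 6.4.1.6, 7.4 and 8.3.5 on the comparator. For this item and item 4, which rule is right is for the sponsor.

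The cost is wording only: Week 0 scores are already scheduled, and concomitant medication is already collected at Visits 1 to 4. Response measured from Week 0 may look less favourable than from screening.
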